649 occur during the Pediatric Transitional Study Session, the data for the Pediatric Transitional Study

650 Session will be reviewed by the DSMB to determine if the RCT Period will commence. If there are  
651 no events for DSMB review during the Pediatric Transitional Study Session, the RCT Period will  
652 proceed prior to review of the data by the DSMB.

653  
654 Adult RCT Period: The Test-Run Period will be completed and the data will be reviewed to verify  
655 safety prior to beginning the Adult RCT Period. The Adult RCT Period will consist of a multi-  
656 center, three-period, random-order, cross-over, feasibility study in 36 adult participants  $\geq 18$  years  
657 old with T1D (18 participants at MGH and 18 participants at Stanford).

658  
659 Four adult participants at MGH will have a Senseonics Eversense CGM sensor implanted and  
660 will participate in a 3-day supervised Test Run. All 4 adult participants will have a designated  
661 contact, who will serve as an emergency contact person in the event study staff are unable to  
662 reach the participant. This Senseonics Eversense Test Run Period will be completed and data  
663 will be reviewed to verify safety prior to beginning the Adult RCT Period at MGH using the  
664 Senseonics Eversense CGM sensor as the input to the iLet. All 18 adult participants at MGH will  
665 have a Senseonics Eversense CGM sensor implanted prior to the initiation of the Adult RCT  
666 Period by the clinical PI at MGH ([name]) or by a study physician under his  
667 supervision. These subjects will use the Senseonics Eversense CGM as the input to the bionic  
668 pancreas instead of the Dexcom G5.

669  
670 All 18 adult participants at Stanford will use the Dexcom G5 CGM as the input to the bionic  
671 pancreas. All other aspects of the Adult RCT Period will remain the same across the two sites.

672  
673 Insulin therapy for each participant will be administered (i) in one period using the iLet in the  
674 insulin-only configuration with the iLet pigtail adapter and the iLet ready-to-fill insulin cartridge,  
675 the Contact Detach infusion set, and the insulin analog that they use for their usual care (either  
676 Humalog or Novolog), (ii) in another period using the iLet in the insulin-only configuration using  
677 the iLet pigtail adapter, the Contact Detach infusion set, and faster insulin aspart (Fiasp) in  

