678 PumpCart, where the pharmacokinetic (PK) parameter for  $t_{max}$  used by the insulin-dosing  
679 algorithm will be set to the same value as is used for Humalog and Novolog (65 minutes), and (iii)  
680 in a third period using the participant's own usual care (UC), where each participant will wear a  
681 CGM. All three experimental periods will be followed by round-the-clock, remote, telemetric  
682 monitoring for hyperglycemia ( $> 300$  mg/dl for  $\geq 90$  minutes) and hypoglycemia ( $< 50$  mg/dl for  $\geq$   
683 15 minutes). The three experimental periods will each have a duration of 7 days. Washout  
684 periods of approximately 7 days in duration will follow the first and second experimental periods  
685 of the Adult RCT Period. The washout period could be as short as 5 days or as long as 9 days,  
686 depending on scheduling of study visits. Of the 36 adult participants, 9 at MGH and 9 at Stanford  
687 will use MDI therapy for their usual diabetes management; the remaining 18 will use insulin pump  
688 therapy. The participants in Stanford Adult RCT Period will wear the Dexcom G5 CGM and the  
689 participants in the MGH Adult RCT Period will wear the Senseonics Eversense CGM. This will  
690 allow us to collect further comparative accuracy data on both the Senseonics Eversense and the  
691 Dexcom G5 in the outpatient setting using the Ascensia Contour Next One meter as the reference.  
692 The cohort of 18 participants at MGH and 18 participants at Stanford might run simultaneously,  
693 might overlap, or might not overlap in time. The Adult RCT Period may take place weeks or  
694 months after the Test-Run Period, so the cohort for the Adult RCT Period may include all, some,  
695 or none of the participants from the cohort of the Test-Run Period.

696  
697 Pediatric RCT Period: The Pediatric Transitional Study Session will be completed and the data  
698 will be reviewed to verify safety prior to beginning the Pediatric RCT Period. The Pediatric RCT  
699 Period will consist of a multi-center, two-period, random-order, cross-over, feasibility study in 20  
700 pediatric participants 6–17 years old with T1D (10 participants at Colorado and 10 participants at

701 Nemours). Insulin therapy for each participant will be administered (i) in one period using the iLet  
702 in the insulin-only configuration with the iLet pigtail adapter and the iLet ready-to-fill insulin  

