### 754 **Major Eligibility Criteria**

755 • Clinical diagnosis of type 1 diabetes for at least 12 months

756 • HbA1c level < 11.0%

757 ○ At least 13 adult participants and 6 pediatric participants in the RCT Period must have  
758 an HbA1c level of 8–11%

759 ○ At least 13 adult participants and 6 pediatric participants in the RCT Period must have  
760 an HbA1c level < 8%

761 • Using an FDA-approved insulin therapy (including Fiasp on MDI therapy for adults, Humalog  
762 or Novolog with CSII or MDI therapy; glulisine users will be excluded)

763 ○ 18 adult participants and 10 pediatric participants must use MDI therapy to manage  
764 their diabetes

765 ○ 18 adult participants and 10 pediatric participants must use CSII therapy to manage  
766 their diabetes

767 • The Adult RCT Period will enroll participants  $\geq$  18 years old

768 ○ Approximately 9 participants in a young adult group (18–24 years old)

769 ○ Approximately 27 participants in an adult group ( $\geq$  25 years old)

770 • The Pediatric RCT Period will enroll participants 6–17 years old

771 ○ 10 participants in a pre-adolescent group (< 12 years old)

772 ○ 10 participants in an adolescent group (12–17 years old)

773

774 *Additional eligibility and exclusion criteria are listed in section 3.2*

775

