### 776 **Sample Size**

777 • The Test-Run Period: 8 participants (age  $\geq$  18 years, MGH only)

778 • The Pediatric Transitional Study Session: 20 participants (~ 6 participants age 6–11 years at  
779 Nemours, ~ 6 participants age 12–17 years at Colorado, and ~ 8 participants age 12–17 years  
780 at Stanford)

781 • Adult RCT Period: 36 participants (age  $\geq$  18 years, 18 participants at MGH, 18 participants at  
782 Stanford)

783 • Pediatric RCT Period: 20 participants (age 6–17 years, 10 participants at Nemours, 10  
784 participants at Colorado)

785

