**2.7. General Considerations**

The study is being conducted in compliance with the policies described in the study policies document, with the ethical principles that have their origin in the Declaration of Helsinki, with the protocol described herein, and with the standards of Good Clinical Practice.

Data will be directly collected in electronic case report forms, which will be considered the source data.

A risk-based monitoring approach will be followed, consistent with the FDA “Guidance for Industry Oversight of Clinical Investigations — A Risk-Based Approach to Monitoring” (August 2013).

The protocol is considered a significant risk device study, due to the fact that the iLet BP system is experimental. Therefore, an IDE from the FDA is required to conduct the study.

998 **CHAPTER 3: PARTICIPANT ENROLLMENT AND STUDY INITIATION**

999 **3.1. Study Population**

1000 Up to 240 individuals with type 1 diabetes may be screened and sign the informed consent form  
1001 for the study so that a minimum of 8 will enter the Test-Run Period in adults, 20 will enter the  
1002 Transitional Study Period in pediatrics, 4 will enter the Senseonics Eversense Test Run and a  
1003 total of 56 will enter the RCT Periods between adults (36 subjects) and pediatrics (20 subjects).  
1004 Screening will continue until the required number is reached. Adult participants in the Test Run  
1005 and the Senseonics Eversense Test Run may also participate in the RCT Period.

1006  
1007 No individuals will be excluded on the basis of gender or race. An equal gender distribution  
1008 between males and females is anticipated.

1009  
1010 The Test-Run Period will be conducted at a single site (MGH) and the Transitional Study Session  
1011 will take place at three sites (Stanford, Nemours and Colorado). It is anticipated that 8 adult  
1012 participants will be in the Test-Run Period and 20 pediatric participants in the Transitional Study  
1013 Session. The Senseonics Eversense Test Run will include 4 adult participants at MGH only. The  
1014 Adult and Pediatric RCT Period will be conducted at four sites in the United States. It is  
1015 anticipated that each adult site (MGH and Stanford) will randomize approximately 18 participants  
1016 into the Adult RCT Period and each pediatric site (Nemours and Colorado) will randomize  
1017 approximately 10 participants into the Pediatric RCT Period. The maximum number of  
1018 randomized participants at a site will be 40.

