#### RCT Period

In the RCT Period, participants for whom eligibility has been verified will complete each of the following phases with the order randomly assigned:

- Adult RCT Period: (i) the iLet in the insulin-only configuration with the iLet pigtail adapter and the iLet ready-to-fill insulin cartridge, the Contact Detach infusion set, and the insulin analog that they use for their usual care (either Humalog or Novolog), (ii) the iLet in the insulin-only configuration using the iLet pigtail adapter, the Contact Detach infusion set, and faster insulin aspart (Fiasp) in PumpCart, where the pharmacokinetic (PK) parameter for  $t_{max}$  used by the insulin-dosing algorithm will be set to the same value as is used for Humalog and Novolog (65 minutes), and (iii) the participant's own usual care (UC), where each participant will wear a CGM.
  - 18 adults at Stanford will use the Dexcom G5 CGM as the input to the iLet and as the CGM during usual care. 18 adults at MGH will use the Senseonics Eversense CGM as the input to the iLet and as the CGM during usual care. All 36 adults will participate in the same three arms, regardless of CGM.

- 1241 • **Pediatric RCT Period:** (i) the iLet in the insulin-only configuration with the iLet pigtail adapter  
1242 and the iLet ready-to-fill insulin cartridge, the Contact Detach infusion set, the Dexcom G5  
1243 CGM, and the insulin analog that they use for their usual care (either Humalog or Novolog),  
1244 and (ii) the participant's own usual care (UC), where each participant will wear a Dexcom G5  
1245 CGM.  
1246

1247 The participant's randomization group assignment is determined by entering the Randomization  
1248 Visit data on the study website. The Jaeb Center will construct a Master Randomization List using  
1249 a block design.  
1250

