### 10.1. Sample sizes

Eight adult participants are expected to complete the Test-Run Period, 4 adults are expected to complete the Senseonics Eversense Test Run, and 36 adult participants will be enrolled in the RCT Period. 20 pediatric participants are expected to complete the Transitional Study Session and 20 pediatric participants will be enrolled in the Pediatric RCT Period. These are convenience samples not based on statistical principles.

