2522 Sensor metrics will be calculated using data from days 2-3. The Senseonics Eversense Test Run will

2523 be completed and the data will be reviewed to verify safety prior to beginning the Adult RCT Period

2524 with the Senseonics Eversense CGM as the input to the iLet.

2525

2526 **10.4. Pediatric Transitional Study Session**

2527

2528 **10.4.1. Summary**

2529 20 pediatric participants (~ 6 participants age 6–11 years at Nemours, ~ 6 participants age 12–17

2530 years at Colorado, and ~ 8 participants age 6–17 years at Stanford) will be randomly assigned to the

2531 following study periods: (1) use of iLet in the insulin-only configuration with the iLet pigtail adapter and

2532 the iLet ready-to-fill insulin cartridge, the Contact Detach infusion set, the Dexcom G5 CGM, and the

2533 insulin analog that they use for their usual care (either Humalog or Novolog), and (2) participant’s own

2534 usual care (UC) where each participant will wear a Dexcom G5 CGM. The two experimental periods

2535 will each span approximately 5 days with a washout period of ~ 3 days in between. The Pediatric

2536 Transitional Study Sessions will be completed and the data will be reviewed to verify safety prior to

2537 beginning the Pediatric RCT Period.

2538

2539 **10.4.2. Outcomes**

- 2540   • The outcomes and analyses will parallel the ones mentioned above for Test-Run Period (i.e,
- 2541    Section 10.2.2) with the exceptions:
- 2542           ○ Sensor metrics will be calculated using data from days 2–5 from each experimental
- 2543            period.
- 2544           ○ The results will be presented by both experimental periods without any formal statistical
- 2545            comparison. Summary statistics appropriate to the distribution will be given separately
- 2546            for the two experimental periods.
- 2547           ○ Questionnaires will be completed at baseline and day 5 of each experimental period.

2548

2549

2550 **10.5. Adult RCT Period**

2551

2552 **10.5.1. Summary**

2553 Forty adult participants (age  $\geq 18$  years) will be enrolled at two sites and will be randomly assigned to  
2554 the following study periods: (1) the iLet in the insulin-only configuration (with the iLet pigtail adapter, the  
2555 iLet ready-to-fill insulin cartridge, and the Contact Detach infusion set) using insulin analog that they  
2556 use for their usual care (either Humalog or Novolog), (2) the iLet in the insulin-only configuration (with  

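### Section 10.5.1 enrols and randomises forty adults in the Adult RCT Period; every other count in the protocol is 36

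*Combined protocol and SAP*

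**What the plan says.** Section 10.5.1 (Adult RCT Period, Summary) begins with "Forty adult participants", who are to be enrolled at two sites and randomly assigned to the study periods.

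The other places that count adults in this period give a different number:

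- Section 10.1 (Sample sizes): "36 adult participants will be enrolled in the RCT Period".
- Section 2.2, Study Design: a "center, three-period, random-order, cross-over, feasibility study in 36 adult participants", with 18 at MGH and 18 at Stanford.
- Section 2.2, therapy split: "Of the 36 adult participants, 9 at MGH and 9 at Stanford" are to be MDI users, and the other 18 pump users.
- Section 2.2, Major Eligibility Criteria: "18 adult participants and 10 pediatric participants must use MDI therapy to manage" their diabetes, with the same numbers required for CSII.
- Section 2.2, Sample Size: "Adult RCT Period: 36 participants".
- Section 3.1 (Study Population): a "total of 56 will enter the RCT Periods between adults (36 subjects) and pediatrics (20 subjects").
- Section 4.3 (Randomization): "All 36 adults will participate in the same three arms".

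The precision statement in 10.5.2.1 is worked for N=36 and N=18. Section 10.1 describes all the sample sizes as convenience samples.

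**The concern.** Sections 10.1 and 10.5.1 are in the same chapter, describe the same period, and both speak of participants being enrolled. The difference therefore cannot be one of enrolled against completed, or screened against randomised.

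Section 10.5.1 introduces the primary adult comparison, so the statistical chapter gives two targets for the number randomised. The randomisation list, the participant flowchart and the detailed analysis plan that Chapter 10 says is still to be written all need a single figure. If four extra adults really are planned, the protocol does not say which site they belong to. Because the CGM is fixed by site, it does not say which sensor they would use. The 18 + 18 therapy quota does not place them either.

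**Working it through.** The sample size rests on no power calculation, so forty cannot be tested against a formula. The check is whether forty or 36 can be rebuilt from the protocol's own component counts.

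| Source | Components | Sum |
|---|---|---|
| 2.2 and 4.3, adults by site | 18 MGH + 18 Stanford | 36 |
| 2.2, adults by insulin method | 18 MDI + 18 CSII | 36 |
| 2.2, adults by age (approximate) | 9 aged 18–24 + 27 aged 25 or over | 36 |
| 3.1, RCT total less children | 56 − 20 | 36 |

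No set of components gives forty. Working in the other direction from forty:

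- RCT total: 40 + 20 = 60, against the stated 56.
- Adults not placed by the site split: 40 − (18 + 18) = 4.
- Adults not placed by the therapy quota: 40 − (18 + 18) = 4.
- Size of the discrepancy: 4 / 36 = 11%.

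Two other routes to forty were considered. Section 3.1 does contain the number 40, but as the maximum randomised at any one site, not as an adult total. The 36 RCT adults plus the 4 in the Senseonics Eversense Test Run also make 40. That run, however, is a separate uncontrolled 3-day period at MGH only, and 3.1 lists its 4 participants apart from the RCT total. Section 10.5.1 describes adults at two sites randomised among three periods.

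The precision statement was also checked in case its widths had been computed with 40 despite the N=36 label. The half-width is the critical value × SD / √N, shown below as the normal and then the t value at 95%.

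| Outcome (SD) | N=36 | N=40 | Stated for N=36 |
|---|---|---|---|
| Time <54 mg/dl (1.0%) | 0.33 to 0.34% | 0.31 to 0.32% | 0.4% |
| Mean glucose (25 mg/dl) | 8.2 to 8.5 mg/dl | 7.7 to 8.0 mg/dl | 10 mg/dl |

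The stated widths exceed both columns, and N=40 fits them less well than N=36. They give no support for forty. Why they are wider than the formula gives is a separate matter.

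**The case against.** The strongest reply is that this is one stray word with an obvious correction. The dedicated sample-size section, the synopsis, 3.1 and 4.3 all state 36, so a careful reader can infer what was meant. Nothing in the analysis depends on forty: the precision statement is labelled N=36, the analysis set is defined by available CGM data, and neither the test order nor the model uses a headcount. That is fair, and it limits the consequence to the enrolment and randomisation target.

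A second reply is that some of the text is loose enough to admit forty:

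- Section 3.3 asks only for roughly half pump and half MDI users, and 10.5.3 for a 1:1 ratio. A 20/20 split would meet both.
- The HbA1c quotas are floors of 13 in each band. They sum to 26 and fit either total.
- Section 3.1 introduces its counts as minimums, gives the adult sites approximate targets of 18, and allows up to 40 per site.

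These points show that more than 36 would not breach every rule. They do not reconcile the figures. The synopsis states the site split and the 18 + 18 therapy quota outright, and the same sentence of 3.1 that speaks of a minimum gives 36 adults within a total of 56. No passage gives forty a reason.

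Nor is the word an extraction fault: it is spelled out in an intact sentence of current text.

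**Conclusion.** The inconsistency is real. Section 10.5.1 states forty; every other adult RCT count in the protocol states 36 or sums to it. The difference is 4 participants, 11% of 36. The conclusion rests only on the protocol's own stated counts and simple addition, with no outside figure.

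The inference that 36 is the intended number is strong but remains an inference, because only the sponsor can confirm that no over-enrolment was planned. The planned analyses are unaffected. The statement should be corrected because it gives the number to be randomised for the primary adult comparison.

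**What to change.** In section 10.5.1, replace the word forty with 36. This is a one-word correction and leaves planned enrolment unchanged.

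If forty was intended as an over-enrolment, state that in 10.5.1 with the reason, and revise section 10.1, the synopsis (2.2), section 3.1 including its total of 56, section 4.3, and the site and therapy quotas so that the four additional adults are placed. That would be a wider protocol change.

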2557 the iLet pigtail adapter, and the Contact Detach infusion set) using faster insulin aspart (Fiasp), where  
2558 the pharmacokinetic (PK) parameter for  $t_{max}$  used by the insulin-dosing algorithm will be set to the same  
2559 value as is used for Humalog and Novolog (65 minutes), and (3) UC (with CGM). Each treatment period  
2560 will last 7 days and there will be approximately 7 days of wash-out in between them.

2561

2562 **10.5.2. Outcomes**

2563

2564 **10.5.2.1 Main Efficacy Outcomes**

2565

2566 All pre-specified main efficacy outcomes in adult subjects will be calculated by pooling data from  
2567 subjects enrolled at the MGH and Stanford sites (and therefore using the Senseonics Eversense and  
2568 Dexcom G5 CGMs, respectively). All reference to CGM data below refers to the CGM system that is  
2569 serving as the input to the iLet.

2570

2571 There are two primary outcome metrics (mean glucose and time  $< 54$  mg/dl) and three treatment  
2572 group comparisons [(2) BP with rapid insulin vs. (3) UC, (1) BP with analog insulin vs. (3) UC, and (2)  
2573 BP with rapid insulin vs. (1) BP with analog insulin], for a total of six statistical comparisons.

2574

2575 To preserve the overall type 1 error, a hierarchical gatekeeping testing procedure will be used. If a  
2576 comparison results in a statistically significant result ( $p < 0.05$ ), then testing will proceed to the next  
2577 one on the list in the following order:

2578

- 2578 1. Mean glucose for (2) BP with rapid insulin vs. (3) UC
- 2579 2. Time  $< 54$  mg/dl for (2) BP with rapid insulin vs. (3) UC
- 2580 3. Mean glucose for (1) BP with analog insulin vs. (3) UC
- 2581 4. Time  $< 54$  mg/dl for (1) BP with analog insulin vs. (3) UC
- 2582 5. Mean glucose for (2) BP with rapid vs. (1) BP with analog insulin
- 2583 6. Time  $< 54$  mg/dl for (2) BP with rapid vs. (1) BP with analog insulin

2584

2585 This process continues iteratively moving to the next combination down on the list until a non-  
2586 significant result ( $p \geq 0.05$ ) is observed, or all six tests are performed.

2587

2588 Regardless of the results of the hierarchical testing, summary statistics appropriate to the distribution  
2589 will be tabulated by treatment period for each metric.

2590

2591 Time  $< 54$  mg/dl and mean glucose will be computed from all available CGM data during days 3-7 for  

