2592 each one of the three treatment periods in the Adult RCT Period. The performance in the iLet periods  
2593 and the difference between the iLet periods and the usual care periods can be compared with historical  
2594 data from previous bionic pancreas trials using previous generations of hardware. If the performance of  
2595 the iLet in this study is comparable to our previous data from trials using the iPhone-based bionic  
2596 pancreas that will support the hypothesis that the iLet is an effective and safe implementation of the  
2597 bionic pancreas. All participants with at least 24 hours of CGM data during days 3-7 of any two of the  
2598 three treatments periods will be included in these analyses. Summary statistics appropriate to the  
2599 distribution for time  $< 54$  mg/dl and mean glucose will be reported for all periods; while a linear model  
2600 that accounts for correlated data from the same subject will be used to compare the treatment periods  
2601 for the Adult RCT Period as described above. From prior experience, the values for time  $< 54$  mg/dl will

2602 have a skewed distribution and for mean glucose a bell-shaped distribution, but the paired differences  
2603 may follow an approximate bell-shaped curve. Residual values for the paired differences will be  
2604 examined for an approximate normal distribution. If values are highly skewed then a rank test will be  
2605 used instead. Additional models will be run to test for any carry-over effects, by adding a treatment by  
2606 order interaction term.

2607  
2608 Scatter plots for time <54 mg/dl and for mean glucose by the three randomized treatment periods in the  
2609 Adult RCT Period will be generated. Additionally, boxplots for all three periods will be generated for both  
2610 outcomes.

2611  
2612 Assuming an effective SD of 1.0% for the pair differences between any one of the three pairwise  
2613 comparisons for time <54 mg/dl, the half width of the associated 95% confidence interval are  
2614 approximately  $\pm 0.4\%$  for N=36 and  $\pm 0.6\%$  for N=18. Similarly, assuming an effective SD of 25 mg/dl for  
2615 mean glucose, the half width of the associated 95% confidence interval are approximately  $\pm 10$  mg/dl  
2616 for N=36 and  $\pm 15$  mg/dl for N=18. Results from the Medtronic 670G Pivotal Trial were used to estimate  
2617 SD for time <54 mg/dl and data from the control period of the JDRF CGM RCT were used to estimate  

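### Adult RCT: the 24-hour CGM minimum qualifies the participant and not the period, so a third period with only a few hours of data can supply a primary value, chiefly a problem for time <54 mg/dl

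*Combined protocol and SAP*

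**What the plan says.** All of this is in section 10.5.2.1 (Main Efficacy Outcomes, Adult RCT Period) unless another section is named.

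- **Who is analysed.** "All participants with at least 24 hours of CGM data during days 3-7 of any two of the" "three treatments periods will be included in these analyses". The requirement is a property of the participant. Once two periods meet it, nothing is said about the third.
- **What is computed.** Time <54 mg/dl and "mean glucose will be computed from all available CGM data during days 3-7 for" "each one of the three treatment periods in the Adult RCT Period". No lower limit on hours is given here.
- **How it is compared.** A linear model "that accounts for correlated data from the same subject will be used to compare the treatment periods". Weighting by hours of data is not mentioned.
- **Safeguard.** Residuals of the paired differences are inspected. "If values are highly skewed then a rank test will be" used in place of the linear model. No numerical trigger is given.
- **Order of testing.** The first test is "Mean glucose for (2) BP with rapid insulin vs. (3) UC"; the second is time <54 mg/dl for the same pair. Testing stops at the first result with p at or above 0.05.
- **Withdrawal (section 9.3).** Data from a participant who withdraws are used up to the point of withdrawal.

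The opening of Chapter 10 promises a separate detailed analysis plan. Its text is not part of the document reviewed.

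**The concern.** A 24-hour threshold is normally there to keep out period values that rest on too little data. Here it does so for two periods and leaves the third open. Someone who completes two periods and withdraws a few hours into day 3 of the last one is included, and those few hours yield a value for each primary outcome. With no weighting stated, that value counts the same as one from a full 120 hours.

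Time <54 mg/dl is the exposed outcome. Over a short window it is either exactly zero or very large. If the short period is BP-Fiasp or UC, it feeds test 2 directly, and failing test 2 closes tests 3 to 6. If it is the Humalog/Novolog BP period, tests 3 to 6 are touched directly, and tests 1 and 2 only through a joint model.

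Two programmers could also build different primary datasets from the same paragraph, and the choice could end up being made after the data are seen.

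**Working it through.** **Inputs from section 10.5.2.1.** N = 36; paired SD 1.0% for time <54 mg/dl; SD 25 mg/dl for mean glucose; significance level 0.05, taken as two-sided because 95% intervals are given. Days 3-7 are 5 days, or 120 h. An episode of 15 minutes matches the minimum duration of a hypoglycemic event in section 10.5.2.2.

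**Assumptions (not in the documents).** A short period of 3 h; a true reduction in time <54 mg/dl of 0.5-0.7 points; within-person glucose SD 45-65 mg/dl with a correlation time of 1-3 h.

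**1. The plan's own precision figures.** Half-width = t(0.975, N-1) × SD / √N.
- Time <54 mg/dl: 0.34 (N=36) and 0.50 (N=18), against the stated 0.4 and 0.6.
- Mean glucose: 8.5 and 12.4 mg/dl, against the stated 10 and 15.

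The stated values are about 18-21% wider and their basis is not given. The point here does not depend on them.

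**2. Weight of one 15-minute low.** Score = 100 × 0.25 / hours observed.

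| Hours observed | Score, time <54 mg/dl | Shift in the mean of 36 |
|---|---|---|
| 120 | 0.21% | 0.006 points |
| 24 | 1.04% | 0.029 points |
| 6 | 4.17% | 0.116 points |
| 3 | 8.33% | 0.231 points |

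At 3 h the score is more than 8 times the assumed paired SD. At 24 h it is about one SD.

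**3. Effect on test 2 if the linear model is kept.** Shifting one difference of 36 by *a* gives SD ≈ √(1 + a²/36).
- 3 h: √(1 + 8.33²/36) = 1.71. With a true reduction of 0.5, t ≈ (-0.5 + 0.231) / (1.71/6) = -0.94. Without the short value, t = -0.5 / (1/6) = -3.0.
- 24 h: √(1 + 1.04²/36) = 1.015, and t ≈ (-0.5 + 0.029) / (1.015/6) = -2.8.

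In 20,000 simulated paired t-tests, test 2, if reached, is significant in favour of the BP as follows (true reduction 0.5 to 0.7):
- no short period: 83-98%;
- one 3 h BP-Fiasp period with one low: 4-27%;
- the same low in 24 h: 78-97%;
- that participant left out of the comparison: 82-98%.

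**4. Effect after the rank-test fallback.** A signed-rank test replaces the linear model. The pass rate is about 82-98% with no short value and about 67-94% with one extreme 3 h value. The loss is 82 - 67 = 15 points at a reduction of 0.5 and 98 - 94 = 4 points at 0.7. Once the value is the largest in rank, making it larger changes nothing.

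**5. Mean glucose.** Under the assumed within-person variation, the SD of a period mean is 30-56 mg/dl from 3 h, 13-30 from 24 h and 6-14 from 120 h. With one 3 h period, effective SD = √[(35 × 625 + (625 - v120 + v3)) / 36], where v is the variance of the period mean.
- Low end: √[(21,875 + 625 - 5.8² + 30.4²) / 36] = 25.5.
- High end: √[(21,875 + 625 - 14.4² + 55.8²) / 36] = 26.6.

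The half-width moves from 8.5 to 8.6-9.0 mg/dl.

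**The case against.** **The plan already has a safeguard.** A value of 8% or more against an SD of 1.0% would stand out in the residual check and trigger the rank test. This largely stands: it turns a collapse in power into a loss of 4-15 points. It does not close the gap, because the trigger has no cut-off and the short value still counts as one full rank.

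**Very short periods should be uncommon.** Failed sensors are to be replaced promptly (sections 5.4 and 6.2.3), offline participants are called every 2 hours (5.5), MGH uses an implanted sensor lasting up to 90 days (6.2.4), and willing participants taken off the BP stay in the trial with all monitoring (8.7.1). This stands as to frequency. Withdrawal under section 9.3 remains an open route.

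**The extreme case is chosen.** This also stands. In simulated traces with an assumed mean of 160 mg/dl and 2% of values below 60 mg/dl, a 3 h record scored 0% in 96% of cases.

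**This is only wording.** The absence of weighting is inferred from silence, and the detailed analysis plan could settle it. But the text is specific about what is computed and from which periods, and followed literally it gives the wrong dataset.

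A reader might go further and infer that one short record decides the gatekeeping sequence. It would do so reliably only if the prespecified residual check were ignored. A reader might also infer that both primary outcomes are equally at risk; step 5 shows that mean glucose, and so test 1, is barely affected. Nor does the gap clearly extend to children: in the two-period pediatric RCT (10.6.2), a requirement of two qualifying periods already demands 24 hours in each.

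**Conclusion.** The concern holds for the Adult RCT. Section 10.5.2.1 lets a third period with a few hours of CGM data contribute a primary value, and no other section prevents it. The consequence is material for time <54 mg/dl and minor for mean glucose. When the short period is BP-Fiasp or UC and contains a low, test 2 loses roughly 4-15 points of power after the rank-test fallback, and much more only if the linear model is retained. A short record without a low scores 0% and slightly favours the arm it belongs to.

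These sizes rest on the plan's SD of 1.0%, N = 36, an assumed true reduction of 0.5-0.7 points and a single 3 h period. How often such periods will occur cannot be taken from the documents and is probably low. This is a correction worth making before analysis. It does not threaten the design.

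**What to change.** In section 10.5.2.1, state that a period contributes a value for time <54 mg/dl and for mean glucose only if it has at least 24 hours of CGM data during days 3-7; that a shorter period is treated as missing in the model; and that the participant's other periods are kept. The rule on two qualifying periods for inclusion can stay. Add a sensitivity analysis that includes every period, however short.

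The cost is one sentence and one extra analysis, with no change to conduct or sample size. The downside is that a very short period leaves the main model and its absence may be informative; the sensitivity analysis addresses that. Section 10.6.2 needs no change if the two-period requirement carries over to the pediatric RCT.
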